11.4.1 Datasets to be analysed, analysis populations

At the end of the study subgroups will be created. We will analyse all outcome variables age, gender, dyspepsia symptom severity (LDQ), other gastrointestinal symptoms, psychological state and gastric function (sensitivity, emptying) at baseline.

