4. STUDY OBJECTIVES

4.1 Overall Objective

The purpose of the present study is to evaluate whether the herbal drug Amara improves the subjective, perceived burden of abdominal symptoms in patients with functional dyspepsia. It will also assess if the treatment is well tolerated. The present study will also investigate psychological and physiological function. This additional information should provide insight into which patients benefit the most from the treatment with Amara. The results of this prospective, open-label therapeutic study will also inform the study design for any subsequent RCT study in functional dyspepsia.

4.2 **Primary Objective**

Document perceived changes in upper gastrointestinal, dyspeptic symptoms reported by patients with functional dyspepsia treated with Amara for 4 weeks, as assessed by the Leuven Dyspepsia Score between visit 1 (off treatment) and 3 (after treatment)..

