4.3 Secondary Objectives

Assess perceived effect of Amara on other gastrointestinal symptoms using validated, patient related outcome measurements (reflux disease questionnaire, IBS Symptom Severity Score).

Assess effect of Amara on (i) visceral sensitivity and (ii) gastric emptying (¹³C-breath test) in patients with functional dyspepsia with validated 400ml Liquid Nottingham Test Meal. Repeat testing will also allow an assessment of reproducibility to be obtained (iii) In a subset of 20 consecutive patients, gastric electrical activity will be measured using the non-invasive Gastric Alimetry System (high-resolution gastric mapping / electro-gastrography) with concurrent heart rate monitoring.

Participants will be asked also to rate their overall satisfaction with Amara and the number that request an additional prescription of Amara for the period after the study will be documented, as an indication of perceived effectiveness.

Additionally, factors that predict the outcome of Amara treatment in functional dyspepsia will be assessed. These factors will include (i) age (ii) sex (iii) severity of dyspeptic symptoms (iv) presence of other gastrointestinal symptoms (v) presence of psychological comorbidity (vi) presence of heightened visceral sensitivity after ingestion of the NTM (vii) abnormal gastric emptying during ¹³C gastric emptying test (viii) compliance with study procedures.

Additionally, the Lüscher Colour Test will be acquired. This non-verbal, non-written test was developed to provide insights into personality and psychological state. This could be of interest in patients with disorders of brain-gut interaction that may not admit to the role of central factors in their illness. Reproducibility of LCT will be documented by repeating the test at Study visit #1 and #2. Correlation with dyspeptic symptoms, psychological or physiological state will be assessed.

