11.4 Planned Analyses

The statistic evaluation will be performed with SPSS (IBM SPSS Statistics, NY: IBM Corp.), version 26 or higher or Graphpad Prism (MacKiev Software), version 9.3.1 or higher or higher for PC or Mac. The demographic data will be analysed with descriptive statistics as average ± standard deviation (SD) for continuous variables and with percentage of total (%) for categorical variables.

Differences between the scores from the primary and secondary endpoint variables – at baseline and after 4-weeks treatment - will be compared initially by t-test if the data is normally distributed and Wilcoxon rank sum test when data are not normally distributed. In addition, if data is normally distributed we will perform univariate and multivariate linear regression analysis in which potential covariates will be considered; confounding will be evaluated by adding these variables to the linear regression model and looking at the change of the regression coefficients. These variables will include participants age, gender, symptom severity, psychological state and gastric function (sensitivity, emptying) at baseline.

In the analysis of the primary outcome two-tailed $p \le 0.05$ will be considered statistically significant. Since the evaluation of the secondary endpoints is purely exploratory, other p-values will be calculated but reported without claiming significance,

Data will be transferred from the REDCap software to the statistics program Prism for evaluation, where data are password protected and only accessible to the persons involved in the study.

All analyses will be performed at Klinik Arlesheim by the research group of [name]. [name], Department of Gastroenterology, Klinik Arlesheim.

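### Subgroups are to be created at the end of the study with no cut-points fixed, and the protocol disagrees with itself on whether the predictors are categories or uncategorised covariates

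*Protocol*

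**What the plan says.** Section 11.4.1 of the protocol consists of two sentences. The first gives the timing: "At the end of the study subgroups will be created". The second gives the factors: "We will analyse all outcome variables age, gender, dyspepsia symptom severity (LDQ), other gastrointestinal symptoms, psychological state and gastric function (sensitivity, emptying) at baseline". A word such as *by* seems to be missing before the list. On that reading, every outcome is examined by seven baseline factors, counting sensitivity and emptying separately. No category boundary is given.

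Section 4.3 lists eight possible predictors of outcome. Four are worded as categories: "iv) presence of other gastrointestinal symptoms (v) presence of psychological comorbidity" and "presence of heightened visceral sensitivity after ingestion of the NTM (vii) abnormal gastric emptying during" the breath test. None has a threshold in the protocol text. Age, symptom severity and compliance are not worded as categories.

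The regression plan treats the factors differently. Section 11.4 says "These variables will include participants age, gender, symptom severity, psychological state and gastric function (sensitivity, emptying) at baseline", and 11.4.2 and 11.4.3 repeat that list with other gastrointestinal symptoms added, again without categories. The limitations in 6.1 describe the same predictor analysis with gastric emptying rate as an example. Section 11.4 attaches a condition to the regression: "if data is normally distributed we will perform univariate and multivariate linear regression analysis". The synopsis states the regression without that condition.

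Three further statements bear on the point. Section 6.1 describes an open, single-arm study. Section 11.4 assigns all analyses to the research group at the site. Section 6.2.3 lists, among the measures against bias, that the statistical analysis plan is contained in the protocol.

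**The concern.** Section 11.4.1 sets the moment at which groups are formed, and that moment comes after the outcomes are known. The trial has no blinded stage, and the analysts belong to the team that runs it. Whoever sets the boundary between low and high sensitivity, or between normal and slow emptying, can already know which boundary gives the larger contrast.

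The second problem is the form of the variables. Under 4.3 the predictor question is answered by comparing groups; under 11.4.2 it is answered by regression on uncategorised covariates. The two can give different answers from the same 60 patients, and the protocol does not say which one leads. If the normality condition in 11.4 fails, the regression falls away, and the subgroup comparison is the only route to the predictor question that the text still describes.

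Section 4.1 expects the additional measurements to "provide insight into which patients benefit the most" from the treatment and the results to inform a later randomised trial. Section 6.1 presents the baseline-factor analysis as relatively less exposed to the placebo effect. A chance subgroup could therefore carry more weight in planning than it deserves.

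**Working it through.** **The plan's own figure.** The protocol gives no number for the subgroup or predictor analysis, so there is nothing to reproduce. The inputs from the protocol are n=60 completers (7.4) and the seven baseline factors in 11.4.1. Normal data, independence between factors and the size of any true correlation are assumptions.

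**Step 1: error for one continuous factor with no true association.** Simulation at n=60, two-group t-test, nominal 5%:

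| How the factor is handled | Share of runs with p<0.05 |
|---|---|
| Kept continuous | about 5% |
| Split at a median fixed in advance | about 5% |
| Best of three quartile cuts, chosen after seeing results | about 12% |
| Best of all cuts between the 20th and 80th percentile | about 28% (28% to 30% across runs) |

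A cut fixed in advance does not inflate the error. The choice after seeing results does.

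**Step 2: all seven factors together.** Gender is binary and has no cut to search, so at most six factors can be searched. Assuming independence, the chance of at least one nominal hit is:

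- no search: 1 − 0.95^7 = 0.30
- best of three cuts: 1 − 0.88^6 × 0.95 = 1 − 0.464 × 0.95 = 0.56
- full search: 1 − 0.72^6 × 0.95 = 1 − 0.139 × 0.95 = 0.87

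The first line is ordinary multiplicity and remains whatever is done about cut-points. The third is an upper bound. Symptom severity, psychological state and sensitivity may well be correlated. Baseline LDQ is also coarse: three items scored 0 to 4 with entry at a total of at least 4 leave the values 4 to 12. That is nine values and eight possible cuts if whole-number totals are used.

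**Step 3: power lost by splitting.** Two-sided 5%, n=60:

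| Assumed true correlation | Continuous | Median split | Top 25% called abnormal |
|---|---|---|---|
| 0.30 | 0.65 | 0.46 | 0.39 |
| 0.35 | 0.79 | 0.59 | 0.51 |
| 0.40 | 0.90 | 0.70 | 0.63 |
| 0.50 | 0.99 | 0.90 | 0.85 |

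For a normal predictor split at quantile q, with z the standard normal quantile at q and φ the normal density, the share of information kept is φ(z)² / (q(1−q)). At the median this is 0.64, so 60 patients act like about 0.64 × 60 = 38. At the 75th percentile it is 0.54, so they act like about 32.

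**Step 4: does the protocol elsewhere fix the boundaries?** The only psychological threshold shown is the HADS exclusion limit. It is above 11 on either scale in 7.1 but at least 14 in 7.2 and the synopsis, which must be reconciled. As an exclusion limit, it is not offered as a subgroup boundary. For the test meal and breath test, 5.2 refers to an appendix SOP for acquisition and analysis. That SOP is not shown and may contain limits.

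**The case against.** The strongest reply is that this is a loosely worded exploratory plan, and that category boundaries are commonly left to a statistical analysis plan. Much of that is fair, and it rules out several stronger readings:

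- **A reader might infer that the subgroups themselves are chosen after the results.** They are not. The factors are named in 11.4.1 and largely repeated in 4.3, 11.4, 11.4.2 and 11.4.3. Only the boundaries are open, and nothing says that they will be chosen on the results.
- **A reader might infer that the protocol has decided to dichotomise continuous tests.** Section 4.3 is the wording of an objective. The analysis sections list the factors uncategorised. Loss of information is a risk left open, and no section proposes a median split.
- **A reader might infer that a false subgroup is almost certain.** That would need an exhaustive search on every factor, including binary gender, and full independence.
- **A reader might infer that no reference limits exist for the physiological tests.** The SOP cannot be inspected, so this cannot be said. Limits taken from it would be external to the results and would remove the problem for those factors.
- **A reader might infer that the trial's main conclusion is affected.** It is not. Sections 11.1 and 11.4 call the secondary outcomes exploratory and claim no significance for them, and the primary test does not use the subgroups.

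The deferral argument is weaker here than usual. Section 6.2.3 places the analysis plan in this protocol, and 11.4.1 does not leave the timing unsaid: it sets it at the end of the study. The conflict between 4.3 and the regression sections also remains, because a later document could not agree with both.

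**Conclusion.** The point holds in moderate form. The protocol postpones the creation of subgroups to the end of an open-label study, fixes no cut-points, and describes the same predictors as categories in one place and as uncategorised covariates in others. If cut-points followed the results, the error for one continuous factor would rise from 5% to between about 12% and 28%. If a continuous factor were split at the median, power at a correlation of 0.35 would fall from about 0.79 to 0.59. These figures assume n=60, normal data and the stated correlation; they show what the wording permits and do not forecast what the team will do. Because the analysis is exploratory and the primary test is untouched, the consequence is limited to how far the predictor results can be trusted when the later randomised trial is designed.

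**What to change.** 1. Delete the sentence in 11.4.1 that creates subgroups at the end of the study.
2. State in 4.3 and 11.4.2 that the predictor analysis of LDQ change uses age, baseline LDQ severity, other symptom scores, HADS, sensitivity and emptying as continuous variables, with sex as binary, and reports estimates with 95% confidence intervals.
3. Remove the condition in 11.4 that the regression is run only if the data are normally distributed. Judge the residuals, and use a rank-based or bootstrap version if they are clearly non-normal. Without this step, the predictor question could lose its regression on the strength of a normality check of the raw data.
4. If a grouped display is wanted, fix its cut-points, with their source (for example, limits in the appendix SOP), before outcome data are reviewed, and label it descriptive.

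The cost is a few sentences in 4.3, 11.4, 11.4.1 and 11.4.2, with no new data or visits. The downside is that the team gives up freely chosen subgroups. Multiplicity across seven factors remains (about 30% for at least one nominal hit if all are null and independent), so the results should still be read as exploratory.

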11.4.2 Primary Analysis

In the intention to treat analysis, all patients who have completed study questionnaires at baseline and after four-weeks of treatment will be included. Following covariates will be included in multivariate models: age, gender, dyspepsia symptom severity (LDQ), other gastrointestinal symptoms, psychological state and gastric function (sensitivity, emptying) at baseline.

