An appointment will be made 2-4-weeks later for the second study visit at which time the ¹³C gastric emptying study will be performed again. The run-in period is 2-4-weeks. This reduces the influence of spontaneous "regression to the mean" (i.e., false positive results).(15)

Gastric motor and sensory function will be assessed by ingestion of the 400ml, 300kcal Nottingham Test Meal (NTM) labelled with ¹³C acetate. This provides both an assessment of patient symptoms / visceral sensitivity to gastric filling with the 400ml liquid nutrient meal and also an assessment of gastric emptying. The 400ml NTM can be ingested by >95% of patients with functional dyspepsia.(19,

24) The ¹³C isotope is not radioactive, it takes 2-hours to complete and this technique is very appropriate for repeated assessment of gastric emptying.(16) In a subset of 20 consecutive patients, gastric electrical activity will be measured before, during and after ingestion of the Nottingham Test Meal using the non-invasive Gastric Alimetry System (high-resolution gastric mapping / electro-gastrography). Concurrent heart rate monitoring will provide an assessment of cardiovagal tone / autonomic nervous function.

The treatment period with Amara drops is four weeks per patient; participants will be instructed to take 10-20 drops of the herbal medicine Amara three times a day before meals over 28 days. This treatment period is in accordance with previous studies for aromatic bitter substances and represents the minimum recommendation for study duration in functional gastrointestinal disorders.(15) During the treatment period patients will record their symptoms using a mobile application (reminder will be sent at 21:00 every day). In addition, patients can note side effects that they perceive to be caused by Amara. If participants do not regularly provide this information, then a team member will call to ask if they have any problems.

At the end of the treatment period the participant will return to Clinic Arlesheim for repeat assessment. The LDQ and other patient related outcomes will be assessed again and ¹³C gastric emptying study will be repeated on treatment.

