At the end of the study, all participants will return the supply of Amara. The study team will assess compliance by counting the empty bottles and weighing partly used bottles. Patients will be asked whether they wish to continue the medication (yes / no). If the response is positive, then ongoing treatment will be recommended. Amara is classified by Swissmedic as dispensing category D available following discussion with specialist without prescription ("Abgabekategorie D: «Abgabe nach Fachgespräch»).

Overall, approximately 30 minutes will be needed to complete the questionnaires on each occasion. The total time required per patient during the study is a maximum of 8 hours (reading documents, filling in questionnaires, gastric emptying study (twice)).

During the period the participants are enrolled in this study no additional outpatient examinations are planned. If, while someone is participating in the study, acute symptom occur and the need arises for early outpatient assessment or inpatient admission to the clinic, the study would be terminated for this subject as of this date.

Limitations:

- The study will provide a prospective assessment of perceived treatment effectiveness; however, a large non-specific (placebo) effect is likely to be present as in any open-label, single-arm study in patients with functional gastrointestinal disease. This limitation is factored into the power calculation which requires at least a moderate treatment effect for Amara to be considered effective. Note that the secondary analysis that will identify baseline factors (e.g., age, sex, symptom severity, gastric emptying rate) that associate with treatment effect will be relatively less sensitive to this confounding factor.

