7.4 Criteria for withdrawal / discontinuation of participants

In emergency situations, where acute symptoms develop or side effects are suspected to be associated with the Amara intake, treatment can be discontinued. The participation can also be terminated by the PI, by the Clinic Arlesheim or by the manufacturer of Amara if there is a suspicion of damage to health caused by the drug or a product defect, respectively. Also, as mentioned before, if there are any signs of patients unwilling to participate in the study it will result in the participant being excluded from the study.

If a participant does no longer fulfil the eligibility criteria at some point of the study, it will lead to the discontinuation of this participant from the study.

Participant recruitment will continue until 60 patients have completed the treatment arm of the study.

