9.2.5 Assessments in participants who prematurely stop the study

Assessments in participants who are withdrawn from the study prematurely, depend on the type and severity of the SAE. Participants who are withdrawn from the study prematurely due to the occurrence of exclusion criteria other than SAEs will not require any follow-up.

See chapter 10. for further information about follow-ups for participants who prematurely stop the study.

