11.4.3 Secondary Analyses

In the per protocol analysis (after four weeks), only patients who have taken at least half of the study medication will be included. Comparisons will be made between scores at study begin and scores after four weeks of treatment. Following covariates will be included in multivariate models: age, gender, dyspepsia symptom severity (LDQ), other gastrointestinal symptoms, psychological state and gastric function (sensitivity, emptying) at baseline.

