11.5 Handling of missing data and drop-outs

Participants who filled out only the screening and/or only the first questionnaire (baseline) will be defined as dropouts. These dropouts will be replaced.

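### The primary LDQ analysis is labelled intention to treat but contains completers only, and treated patients who leave are replaced; if those doing worse leave more often, the mean improvement is overstated

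*Protocol*

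**What the plan says.** - **Primary set (Protocol 11.4.2):** "In the intention to treat analysis, all patients who have completed study questionnaires at baseline and after four-weeks of treatment will be included".
- **Per-protocol set (11.4.3):** "only patients who have taken at least half of the study medication will be included".
- **Leavers (11.5):** "Participants who filled out only the screening and/or only the first questionnaire (baseline) will be defined as dropouts", followed by "These dropouts will be replaced". No distinction is made between leaving in the run-in and leaving after the first dose.
- **Recruitment (7.4):** "Participant recruitment will continue until 60 patients have completed the treatment arm of the study".
- **One way out of the study (6.1):** if acute symptoms call for "early outpatient assessment or inpatient admission to the clinic, the study would be terminated for this subject as of this date". Section 7.4 also allows treatment to be stopped for acute symptoms or suspected side effects.
- **After early stopping (9.2.5):** "Assessments in participants who are withdrawn from the study prematurely, depend on the type and severity of the SAE". Withdrawals for other exclusion criteria need no follow-up. A 4-week LDQ is not requested in either case.
- **Data of withdrawn patients (8.5):** what was collected before withdrawal stays in use.
- **Measures against loss:** "If participants do not regularly provide this information, then a team member will call to ask if they have any problems" (6.1). Section 9.3.2 adds an e-mailed questionnaire link before visit 3 and allows the forms to be completed at the visit.

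Section 6.2.3 says that the statistical analysis plan is contained in the protocol, so these rules are fixed here rather than deferred.

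**The concern.** An intention-to-treat set should not depend on what happens after treatment starts. Membership of this one depends on having a 4-week questionnaire. A patient who takes Amara and leaves before week 4 is missing from the primary set, is replaced by someone else, and has no 4-week score for the per-protocol comparison. Replacement restores the count of 60, and with it the precision, but it does not restore the missing outcomes.

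In a single-arm study no control group with similar attrition can offset the shift. Section 11.1 says the study is meant to give an idea of the effect size, so a distorted mean change damages its main product. Sections 11.4.2 and 11.5 also leave no place for the withdrawn patients' data that 8.5 says will be used.

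**Working it through.** **Inputs from the protocol:** 60 completers (7.4); two-tailed test at 0.05 (11.4); standardised effect 0.4 (11.2). The plan has no attrition figure to reproduce.

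**Assumptions, not in the documents:** 5%, 10% or 20% of treated patients leave; the odds of leaving are multiplied by 1.65 or 2.72 per SD of worse outcome (slope b = 0.5 or 1).

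**Step 1: which patients remain.**

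| Patient | Primary set | Per-protocol set | Replaced |
|---|---|---|---|
| Leaves in run-in, no Amara | no | no | yes |
| Takes Amara, no 4-week form | no | no | yes |
| Stops or takes few drops, returns 4-week form | yes | only if at least half taken | no |
| Returns form, at least half taken | yes | yes | no |

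The second row is the problem. The first row does no harm.

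**Step 2: bias in the mean.** Let W ~ N(0,1) be worsening relative to the average patient, and P(W) = 1/(1+exp(−(a+bW))) the chance of leaving. Choose a so that the average of P equals the share leaving, q. Then

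bias = −E[W(1−P)]/(1−q) = q × (completer mean − leaver mean),

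with both means on the improvement scale. For b = 1 and q = 0.10, a = −2.56, the completer mean is +0.091 and the leaver mean −0.817, so the bias is 0.10 × (0.091 + 0.817) = 0.091 SD.

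| q | bias, OR 1.65 | bias, OR 2.72 |
|---|---|---|
| 5% | 0.025 | 0.047 |
| 10% | 0.049 | 0.091 |
| 20% | 0.096 | 0.173 |

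The bias does not depend on the true mean change, because a is recalibrated to q. With OR 1 it is zero; with the inverse odds ratios it has the same size and the opposite sign.

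**Step 3: with the protocol's 0.4.** At OR 2.72 the completer mean is 0.447, 0.491 and 0.573 SD. The standardised effect is larger (0.456, 0.509, 0.608) because selection also shrinks the SD, to 0.980, 0.965 and 0.943. The figures for the mean are the ones that describe overstatement of the mean.

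**Step 4: false-positive rate with no true change.** One-sample t-test, 59 df, noncentrality √60 × bias/SD. For OR 2.72 and q = 20%: 7.746 × 0.173/0.943 = 1.42, giving 28.8%.

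| q | OR 1.65 | OR 2.72 |
|---|---|---|
| 5% | 5.4% | 6.6% |
| 10% | 6.6% | 11.1% |
| 20% | 11.6% | 28.8% |

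For comparison, a non-specific shift of 0.2 SD with no attrition gives 33% rejection at n = 60.

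**Step 5: entering no change for leavers.** With a true 0.4 and OR 2.72 the mean becomes (1−q) × completer mean: 0.95 × 0.447 = 0.425, 0.90 × 0.491 = 0.442, 0.80 × 0.573 = 0.459. This removes about half to two thirds of the bias. With no true change it leaves rejection at about 6%, 11% and 28% (simulation), so it helps the estimate but does not protect the test.

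**Step 6: a tipping-point example.** Suppose 60 completers improve by 0.40 SD and 15 leavers worsen by 0.40 SD, with SD 1 in each group. The pooled mean is (24 − 6)/75 = 0.24. The pooled variance is (59 + 14 + 60×0.16² + 15×0.64²)/74 = 1.090, so SE = 1.044/√75 = 0.1206. Then t = 1.99, against a critical value of 1.99, so significance is just lost.

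**The case against.** **Attrition may be small.** Treatment lasts four weeks, with daily reminders, calls to patients who stop reporting, and forms that can be completed at the visit. This stands. At 5% leaving, the bias is below 0.05 SD under either odds ratio, and no document supports 20% leaving or any particular strength of selection.

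**The placebo response is probably the larger bias.** The protocol says so in substance (6.1, 11.2) and says its design does not allow efficacy to be evaluated. This also stands, and it makes the false-positive figures secondary, since a true mean change of zero is not what the protocol expects.

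**Stronger readings a reader might infer, which the documents do not support:**
- *That the later trial would be undersized by a calculable percentage.* That study is to be randomised and placebo-controlled (11.2), and so sized on a between-group difference. A single-arm change sums placebo and treatment effects (5.1) and cannot supply that difference, with or without dropout.
- *That the bias must favour Amara.* The exit rule in 6.1 covers acute symptoms generally and is not limited to dyspepsia. Outcome-related leaving is plausible, not established.
- *That poor compliers are excluded from the primary set.* They stay if they return the 4-week form.
- *That no analysis of any kind covers everyone treated.* The safety analysis (11.4.5) is not limited to completers; the gap concerns the LDQ.

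**Conclusion.** The point holds from the text alone as to the mislabelled set, the replacement of treated leavers, the absence of a secured 4-week LDQ after early stopping, and the conflict of 8.5 with 11.4.2 and 11.5. The direction of bias is conditional: upward if patients who do worse leave more often, nil if leaving is unrelated to outcome, downward if patients who feel well leave.

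Its size cannot be fixed from the protocol. Under the assumed odds ratios of 1.65 to 2.7 per SD, the mean is overstated by about 0.025–0.047, 0.05–0.09 and 0.10–0.17 SD at 5%, 10% and 20% leaving. With no true change, rejection is 5–7%, 7–11% and 12–29% instead of 5%. The main harm is to the estimate. This should be fixed, but it is not a fatal flaw.

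**What to change.** 1. Define the primary set as all patients who took at least one dose of Amara and have a baseline LDQ.
2. State in 9.2.5 that treated patients who stop early are sent the existing 4-week questionnaire link unless they withdraw consent.
3. Limit replacement without further analysis to patients who leave before the first dose. Keep treated leavers in the analysis even if recruitment is topped up to 60 completers.
4. Name one primary method for 4-week LDQ values still missing, for example multiple imputation from the baseline LDQ and the daily symptom record kept during treatment. The protocol does not say whether that record holds the LDQ items, so this needs checking first. Add no change for leavers and a tipping-point analysis as sensitivity analyses.
5. Rename the present set a completer analysis, report it as a sensitivity analysis, and give the numbers treated, lost and replaced, with reasons.
6. Reconcile 8.5 with 11.4.2 and 11.5.

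**Cost:** an amendment to 8.5, 9.2.5, 11.4.2 and 11.5 (with ethics committee approval if judged substantial), a few extra questionnaires and some added analysis. The target of 60 completers in 7.4 can stay. The estimated improvement may turn out smaller.
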